2.6 Cytarabine

Cytarabine is available commercially.

Cytarabine is a deoxycytidine analog that is metabolized to cytarabine triphosphate, a substance that inhibits DNA polymerase. It is S phase specific, and thus affects DNA synthesis. It has an initial plasma half-life of about 15 minutes, with a secondary phase of about 2 hours, and is rapidly catabolized by hepatic cytidine deaminases to Ara-U.

Cytarabine injection, an antineoplastic is a sterile solution of cytarabine for intravenous administration. Each mL contains 20 mg cytarabine in 100 mg (20 mg/mL) single dose vials and 100 mg cytarabine in 2 g (100 mg/mL) single dose vial.

Cytarabine injection 100 mg/5 mL is a sterile solution for intravenous administration. Each mL contains 20 mg cytarabine USP, and the following inactive ingredients: sodium chloride 6.8 mg and Water for Injections qs. When necessary the pH is adjusted with hydrochloric acid and/or sodium hydroxide to a pH of 7.7.

Chemical stability studies were performed by ultraviolet assay on cytarabine injection in infusion solutions. These studies showed that when cytarabine injection was added to Water for Injection, 5% Dextrose in Water or Sodium Chloride Injection, 94% to 96% of the cytarabine was present after 192 hours storage at room temperature. Parenteral drugs should be inspected visually for particulate matter and discoloration, prior to administration, whenever solution and container permit.

2.7 Uproleselan injection, 50 mg/mL

The investigational product, uproleselan injection, 50 mg/mL, is a sterile, isotonic solution for IV administration. The drug substance is present as the sodium salt; however, the solution concentration is based on the free-acid active moiety. The formulation contains precedented compendial excipients. The sodium content of the formulation is 3.3 mg/mL. The clinical product formulation includes 10 mM Tris buffer to stabilize the pH at 7.4 (6.4 to 8.4).

Uproleselan injection is supplied in single-dose vials at a concentration of 50 mg/mL. Uproleselan injection 50 mg/mL is stored per the specified conditions on the label, either frozen (10 °C to -25 °C) or refrigerated (2-8°C), prior to administration. The frozen product can appear as a homogenous solid, a striated solid, or as a super-cooled liquid. When using frozen supply, vials should be brought to room temperature before dose preparation. Upon thawing, the product should be gently inverted 4 to 5 times to ensure homogeneity of the solution. The thawed solution is clear, colorless to slightly yellow, and free from visible particulates. Reconstitution and dilution are not necessary. Dilution up to 10X may be performed with normal saline.

Uproleselan injection should be administered IV into a peripheral line, a central catheter, or a peripherally inserted central line catheter (PICC).

Infusion should take place at a steady rate over a period of 20 minutes using a syringe pump or IV pump. Microbore tubing is preferred. In-line filtration is highly recommended.

Compatibility with other therapeutic agents has not been determined; therefore, uproleselan injection should be administered via a separate IV line and should not be administered concurrently with anything other than saline. If a flush is used, saline flush is preferred.

When prepared in syringes or intravenous (IV) bags without an administration set attached, uproleselan may be stored refrigerated up to 72 hours prior to administration or up to 24 hours at controlled room temperature prior to administration. Administration sets manufactured from materials of construction other than polyvinyl chloride (PVC) with di(2-ethylhexyl)phthalate (DEHP) can be primed up to 72 hours before dosing if stored refrigerated or up to 24 hours before dosing if stored at controlled room temperature. Intravenous lines consisting of PVC with DEHP should be avoided when possible. If PVC with DEHP administration sets must be used they should be primed with uproleselan solution no more than 2 hours before dosing. It is highly recommended that uproleselan prepared prior to administration be refrigerated until 1 hour prior to dosing.

Uroleselan is to be kept in a locked and secured storage facility, accessible only to those individuals authorized by the principal investigator (PI).

3.0 PATIENT SELECTION

3.1 Inclusion Criteria:

1. Patients with a diagnosis of treated secondary-AML (TS-AML) who have not received therapy for their AML will be eligible.
2. TS-AML is defined as AML arising from a previously treated antecedent myeloid neoplasm (myelodysplastic syndrome or myeloproliferative neoplasm that has been previously treated with hypomethylating agents).
3. Patients must be at least 7 days from their last therapy for the antecedent myeloid neoplasm
4. Age ≥ 18 years.
5. Adequate organ function as defined below:
 - liver function (total bilirubin ≤ 2 mg/dL, AST and/or ALT $\leq 3 \times$ ULN – or $\leq 5 \times$ ULN if related to leukemic involvement)
 - kidney function (creatinine $\leq 1.5 \times$ ULN).
 - known cardiac ejection fraction of $>$ or $= 45\%$ within the past 6 months
6. ECOG performance status of ≤ 2 .
7. A negative urine or serum pregnancy test is required within 1 week for all women of childbearing potential prior to enrolling on this trial.
8. Patient must have the ability to understand the requirements of the study and informed consent. A signed informed consent by the patient is required prior to their enrollment on the protocol.

3.2 Exclusion Criteria

1. Pregnant women are excluded from this study because the agents used in this study have the potential for teratogenic or abortifacient effects. Because there is a potential risk for adverse events in nursing infants secondary to treatment of the mother with the chemotherapy agents, breastfeeding should also be avoided.

2. Uncontrolled intercurrent illness including, but not limited to active uncontrolled infection, symptomatic congestive heart failure (NYHA Class III or IV), unstable angina pectoris, clinically significant cardiac arrhythmia, or psychiatric illness/social situations that would limit compliance with study requirements.
3. Patients with documented hypersensitivity to any of the components of the chemotherapy program.
4. Men and women of childbearing potential who do not practice contraception. Women of childbearing potential and men must agree to use contraception prior to study entry and for the duration of study participation.
5. Prior treatment with uproleselan.
6. Patients with a diagnosis of acute promyelocytic leukemia (AML-M3) will be excluded from this study.

4.0 TREATMENT PLAN

This is a single arm phase Ib/II study in which patients will be treated with uproleselan given intravenously, combined with cladribine, (2-CDA, given intravenously [IV]) in combination low dose cytarabine (LDAC, given subcutaneously [SQ]) as induction therapy, followed by up to 6 cycles of consolidation/maintenance therapy composed of 2-CDA + LDAC (according to schema below) also in combination with uproleselan. In patients who do not achieve CR/CRi/MLFS after cycle 1, an additional course of re-induction with 2-CDA+LDAC+uproleselan may be given.

Treatment will be continued during the duration of the study unless patient exhibits evidence of clinically significant treatment failure, clinically significant disease progression, unacceptable toxicity, or if the investigator determines that discontinuation is in the best interest of the patient. Patients who do not achieve at least MLFS after two cycles of therapy will be taken off study. Relapsing patients may remain on the study if participation in the study is still providing disease control or clinical benefit and is considered in the best interest of the patient after discussion with the principal investigator.

Patients will be treated with the study drugs per protocol, based on the calculation of the patient's body surface area (BSA). The BSA will be calculated before each cycle and will be based on the patient's height and weight.

Patients will be instructed to self-administer cytarabine at home unless hospitalized and return unused drug in accordance with institutional guidelines. All induction and consolidation intravenous infusions will be administered at MD Anderson Cancer Center (MDACC) or at the MDACC Houston Area Locations (HALs).

The primary objective is to determine the safety of this combination and also to determine efficacy in achieving CR, CRi; and prolonging RFS and OS. All patients will be registered for the protocol via the Clinical Oncology Research (CORE) system at MDACC (single institution study).

The study will have 2 dose levels during lead-in, followed by an expansion cohort of 25 patients at the safe and tolerable dose level. All patients will be treated with the RP2D of uproleselan of 800 mg IV on D1 and then IV q12 hours on D2-12.

During safety lead-in, we will use the BOPIN design (see section 8.0) to identify the RP2D of the combination therapy. During phase II, 25 additional patients will be enrolled at the RP2D level to confirm safety and to assess preliminary efficacy.

4.1 Treatment Schema (4-week cycles +/- 7 days)

4.1.1 Induction therapy will consist of:

- A. Uproleselan 800 mg IV on D1 and then 800mg IV Q12 hours (+/- 2 hours) on D2-12 approximately 1 hour prior to cladribine (+/- 15 minutes).
- B. Cladribine at the assigned dose level IV over approximately 1 to 2 hours, daily on days 1-5 combined with cytarabine at the assigned dose level SQ twice daily on days 1-10. The cytarabine should be administered approximately 3-6 hours following the start of the cladribine infusion.
 - 4.1.1.1 Patients who do not achieve a CR or CRI after cycle 1 may proceed with a second induction cycle as noted in Table 2 below.
 - 4.1.1.2 Patients who do not achieve a CR or CRI after cycle 2 may continue on protocol (as shown in Table 2) as long as the patient is deriving clinical benefit in the opinion of the investigator.

4.1.2 Consolidation/Maintenance therapy will consist of:

- (A) Uproleselan 800 mg IV on D1 and then 800mg IV Q12 hours (+/- 2 hours) on D2-12 approximately 1 hour prior to cladribine (+/- 15 minutes). In patients who have achieved at least CR/CRI or morphologic leukemia-free state, uproleselan will be given ONCE daily on D1-12.
- (B) Cladribine at the assigned dose level IV over 1 to 2 hours, daily on days 1-3 combined with Cytarabine at the assigned dose level SQ twice daily on days 1-10. The cytarabine should be administered 3-6 hours following the start of the cladribine infusion.

Table 1. Dose Escalation Table		
Dose level	Cladribine (mg/m ² IV daily on days 1-5)*	Cytarabine (mg SQ twice daily on days 1-10)
1	5	20
-1	3.75	15

One cycle of therapy is considered 4 weeks. Subsequent cycles may be started within 4-7 weeks after the start of the previous cycle depending on hematopoietic recovery and resolution of toxicities in the judgment of the

treating physician. Subsequent cycle delay beyond 7 weeks may be allowed after discussion with the principal investigator and documentation of the discussion.

Patients with progressive or proliferating disease requiring initiation of a subsequent cycle of chemotherapy prior to day 28 of a previous cycle may start therapy no earlier than day 21 of a previous cycle after discussion with the principal investigator and documentation of the discussion.

The flow of treatment schema is outlined in the table below:

Table 2.

Cycle Number	Induction	Consolidation
1	Cladribine IV daily on days 1-5 Cytarabine SQ twice daily on days 1-10 Uproleselan 800 mg IV on D1 and then 800mg IV Q12 hours on D2-12	NOT APPLICABLE
2	<IF RE-INDUCTION IS INDICATED> Cladribine IV daily on days 1-5 Cytarabine SQ twice daily on days 1-10 Uproleselan 800 mg IV on D1 and then 800mg IV Q12 hours on D2-12	<IF PT ACHIEVES CR or CRi or MLFS after CYCLE 1> Cladribine IV daily on days 1-3 Cytarabine SQ twice daily on days 1-10 Uproleselan 800 mg IV daily on D1-12
3 - 6		Cladribine IV daily on days 1-3 Cytarabine SQ twice daily on days 1-10 Uproleselan 800 mg IV daily on D1-12

4.1.3 Definition of DLT

Dose Limiting Toxicity (DLT) - DLT will be graded according to the NCI Common Terminology Criteria for Adverse Events (CTCAE, version 5) by organ system. DLT will be defined as adverse events during cycle one.

A) Grade 3 or greater, non-hematologic toxicities **at least possibly related to study treatment** will be considered DLTs. Any Grade 3 nausea, vomiting or diarrhea that requires hospitalization, tube feeding or TPN is a DLT unless definitely attributed to a different cause. As the following are common events in patients with leukemia (> 50%), they will not be used for the definition of DLT: prolonged myelosuppression (grade 3 - 4), neutropenic fever without infection (grade 3), non-neutropenic fever (grade 3), infections with grade 3 and 4 neutropenia [exception – see bullet E below], infections without neutropenia (grade 3) [exception – see bullet E below], readmission associated with NCI grade 3 toxicity, cytopenias not

resulting in death, transfusions of platelets and packed RBCs (grade 3), low blood pressure due to dehydration requiring fluid replacement, abnormalities of LDH (lactate dehydrogenase) and alkaline phosphatase, tumor lysis syndrome related to disease bulk (grade 3-4), disturbances in electrolytes (magnesium, phosphorus, calcium), alopecia, nausea and vomiting (if manageable with supportive care measures). Grade ≥ 4 non-hematologic organ toxicities that are not definitely attributed to another reason will be considered DLTs.

- B) Grade 4 neutropenia or thrombocytopenia lasting beyond day 42 of the cycle in the absence of leukemia. Anemia will not be considered a hematologic DLT.
- C) Any adverse reaction that leads to dose reduction or withdrawal should be considered a DLT. For the following, if not definitively related to disease or concomitant drugs: Grade 3 transaminitis (AST/ALT) elevation that does not return to Grade 1 or lower within 72 hours is a DLT. Grade 3 electrolyte abnormalities (Na, K, Cl, CO₂, Ca, Mg, phosphate) that do not return to Grade 1 or lower within 72 hours is a DLT.
- D) Any grade 3 liver abnormality conforming to Hy's Law will be considered a DLT unless it resolves within 72 hrs. The criteria for Hy's Law are as follows: (1) 3-fold or greater elevations above the ULN of ALT or AST; (2) concomitant elevation of serum total bilirubin to >2 x ULN, without findings of cholestasis (or elevated serum ALP), and (3) No other reason can be found to explain the combination of increased transaminases and bilirubin, such as viral hepatitis A, B, or C; preexisting or acute liver disease; or another drug capable of causing the observed injury
- E) Any grade 3 infection lasting for more than 7 days without improvement when leukemia is in remission is considered a DLT. Any grade 3 bleeding with thrombocytopenia worsening and uncontrolled by appropriate measures when leukemia is in remission is considered a DLT.

4.2 Supportive Care Measures during treatment

Necessary supportive measures for optimal medical care can be given throughout the study as indicated by the treating physician's assessment of the patient's medical need and by the institutional guidelines. Administration of antiemetics during drug administration and throughout treatment course is permitted as clinically indicated and according to departmental guidelines. Blood products should be transfused as indicated and in accordance with institutional guidelines. The use of other anti-leukemia therapy is not allowed during the course of therapy except for hydroxyurea which is allowed for the first 3 cycles of therapy only. Concomitant intrathecal chemotherapy and/or radiation therapy is permitted where indicated in patients with extramedullary disease.

4.2.1 Hematopoietic growth factors

Hematopoietic growth factors such as filgrastim or pegfilgrastim (GCSF) is permitted as clinically indicated at the discretion of the treating physician.

4.2.2 Infection prophylaxis

Antibacterial, antifungal, and antiviral agents may be used in patients being treated on this study in accordance with the standard of care.

4.3 Duration of Therapy

In the absence of treatment delays due to adverse events, the treatment will be administered approximately once every 4 weeks for up to 6 cycles. The patient will continue on the study unless one of the following criteria applies:

- Clinically significant progressive disease as defined by Modified International Working Group Criteria (see section 9) without evidence of clinical benefit. (Patients who have not had at least 50% reduction in bone marrow blasts by 4-6 cycles would be considered not to have clinical benefit and will come off study).
- Possibility of undergoing allogeneic bone marrow transplant.
- Intercurrent illness that prevents further administration of treatment.
- Patient request.
- Unacceptable toxicity.
- Need for further, alternative treatment.
- General or specific changes in the patient's condition that render the patient unacceptable for further treatment in the judgment of the investigator or treating physician.

5.0 PATIENT EVALUATION

AML patients are typically admitted for the first month of therapy in the hospital and monitored daily for toxicities by oncologists. Following the first cycle, they are seen frequently by mid-level providers or oncologists throughout their treatment course. Toxicities are assessed by history, physical, and review of laboratory and radiologic data. These are reported to the research nurse coordinator, treating MD, and/or PI, given attribution and documented in the EMR on study interim notes. Toxicity logs will be utilized to record adverse events.

5.1 Pretreatment Evaluation. (To be completed within 14 days of study entry unless otherwise indicated)

- a. History and physical examination, including vital signs, height, weight and performance status.

- b. Bone marrow aspirate and/or biopsy (Cytogenetics, flow cytometry and molecular studies performed as appropriate) within 7 +/- 3 days of treatment start.
- c. Biomarker testing for correlative studies will be collected as described in section 5.4.
- d. CBC with differential (within 3 days) (differential not required if WBC $\leq 0.5 \times 10^9/L$).
- e. Serum chemistry: BUN, creatinine, bilirubin, AST and/or ALT, Magnesium, glucose, uric acid, (within 3 days).
- f. Serum coagulation studies: PT/PTT/INR; (within 3 days)
- g. Urine or serum pregnancy test within one week for women of childbearing potential.
- h. Signed informed consent.

5.1 During Treatment Evaluation (Cycle 1)

- a. Physical examination (including vital signs) 3 times per week.
- b. CBC with differential (differential not required if WBC $\leq 0.5 \times 10^9/L$), 3 times per week (or as clinically indicated) until remission, then every 2 to 4 weeks during active treatment, and then every 4 to 8 weeks thereafter as long as they are on study.
- c. Serum chemistry profile (including uric acid) 3 times per week for the first 4 weeks and then every 2 to 4 weeks during active treatment.
- d. Biomarker testing for correlative studies on D1, 5, 10, and 12 of cycle 1 as summarized in section 5.4.
- e. Evaluation of toxicity assessment prior to each cycle.

5.2 During Treatment Evaluation (Cycle 2 and beyond).

- a. Physical examination (including vital signs, weight, performance status) prior to each cycle.
- b. CBC with differential (differential not required if WBC $\leq 0.5 \times 10^9/L$), at least 1-2 times per week (or as clinically indicated) until remission, then every 2 to 4 weeks during active treatment, and then every 4 to 8 weeks thereafter as long as they are on study.
- c. Serum chemistry profile at least once weekly until remission and then every 2 to 4 weeks during active treatment.
- d. Evaluation of toxicity assessment prior to each cycle.

5.3 Outcome assessments

- a. Bone marrow aspiration and/or biopsy starting on day 21 (+/- 7 days) of therapy and then every 2 weeks (+/- 7 days) as required by leukemia evolution until remission or non-response. Bone marrow tests may be ordered more frequently as indicated by changes in peripheral blood counts. No repeat bone marrow is necessary if non-response or progressive disease can be unequivocally diagnosed from peripheral blood tests or, in patients with a

WBC <0.4 x10⁹/L, if the bone marrow is considered non-contributory by the investigator at any point.

b. Patients will be followed for relapse and survival every 6 to 12 months after completion of active treatment and while still on study or be enrolled on the leukemia department long-term follow-up umbrella protocol. This may be completed by phone call if the patient is not coming for routine visits.

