Multi Lean Desktop (version 2.1.0) was used to generate the toxicity and futility stopping boundaries and the operating characteristics table.

ANALYSIS PLAN

Summary statistics will be provided for continuous variables. Frequency tables will be used to summarize categorical variables. The overall response rate will be estimated along with the 95% credible interval. Similar analyses will be performed for other binary outcomes such as CR, CRi, etc. Overall survival (OS) is defined as the time interval between treatment start and the date of death or last follow-up, whichever occurred first. Remission duration (CRd) is defined, within patients who achieve CR/CRi, the time interval between the date of CR/CRi and the date of disease relapse, death or last follow-up, whichever occurred first.

Progression-free survival (PFS) is defined as the time interval between treatment start and the date of death, relapse or last follow-up, whichever occurred first. Kaplan-Meier method will be used to assess OS, CRd and PFS probabilities. Data from all subjects who receive any study drug will be included in the safety analyses. Subjects who entered the study and did not take any of the study drugs and had this confirmed will not be evaluated for safety. The severity of the toxicities will be graded according to the NCI CTCAE v5.0 whenever possible. We will follow standard reporting guidelines for adverse events. Safety data will be summarized by category, severity and frequency.

Cohort Summaries

The Investigator is responsible for completing toxicity summary reports and submitting them to the IND office Medical Affairs and Safety Group, for review and approval. These should be submitted as follows:

Phase 1B:

After the first 3 evaluable patients, complete cycle 1 of study treatment, and every 3 evaluable patients thereafter, prior to expanding/changing dose levels, or opening Phase II.

Phase II:

After the first 5 evaluable patients per cohort, complete cycle 2 of study treatment, and every 5 patients thereafter, until enrollment is complete.

A copy of the summary report should be placed in the Investigator's Regulatory Binder under "sponsor correspondence".

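### After treatment, relapse checks are stated in two unreconciled ways, and a phone contact with no blood count can extend remission duration and PFS

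*Combined protocol and SAP*

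**What the plan says.** Three parts of the protocol bear on how relapse is found and dated after treatment.

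- **Blood counts.** For the CBC with differential, 5.1(b) (cycle 1) and 5.2(b) (cycle 2 onward) both specify, once remission is reached: "then every 2 to 4 weeks during active treatment, and then every 4 to 8 weeks thereafter as long as they are on study".
- **Relapse follow-up.** Section 5.3(b) is the only schedule that names relapse: "Patients will be followed for relapse and survival every 6 to 12 months after completion of active treatment and while still on study". It offers an alternative, "or be enrolled on the leukemia department long-term follow-up umbrella protocol", and adds: "This may be completed by phone call if the patient is not coming for routine visits". Section 5.3(a) schedules marrows only until remission or non-response, but also says: "Bone marrow tests may be ordered more frequently as indicated by changes in peripheral blood counts". It accepts that no repeat marrow is needed when "progressive disease can be unequivocally diagnosed from peripheral blood tests".
- **Analysis.** Section 8 defines CRd as "the time interval between the date of CR/CRi and the date of disease relapse, death or last follow-up, whichever occurred first". PFS has the same three end points, counted from treatment start. The estimator is stated as: "Kaplan-Meier method will be used to assess OS, CRd and PFS probabilities". Section 9.1.8 defines relapse-free survival differently, ending it at the first objective documentation of relapse, or at death.

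**The concern.** Kaplan-Meier takes each relapse date as given and treats each censored patient as relapse-free up to the censoring date. Both need an objective check behind them. A patient who no longer attends, or who has moved to the umbrella protocol, may have none specified. The 4-to-8-week count lasts only while the patient is on study. The local blood work described in 5.5 is for the treatment period, between cycles.

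For such a patient two things are undefined. First, a phone contact can serve as last follow-up and so extend relapse-free time with no count or marrow to support it. Second, if the call reveals a relapse, the plan does not say whether the relapse date is the call or the date of diagnosis. Dating it at the call lengthens CRd and PFS, and the error always runs in the flattering direction. OS is not affected, because a phone call can establish vital status.

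**Working it through.** The plan gives no event count, precision or target for CRd or PFS, so there is no figure of its own to reproduce. The check asks how much each schedule would delay the recorded relapse date.

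**Inputs from the protocol.** Blood counts every 2 to 4 weeks on treatment (3 used), then every 4 or 8 weeks (5.1(b), 5.2(b)). Contact every 6 or 12 months (5.3(b)). Up to 6 cycles (4.3), started 4 to 7 weeks apart (4.1). Death counts as an event (section 8).

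**Assumptions not in the protocol.** Relapse times are exponential from CR, with true median 4, 6, 9 or 14.7 months. Only the last appears in the protocol (2.3), for a different population. Median time from relapse to death is 3 months. CR follows cycle 1, so five further cycles end treatment 20 weeks (4.6 months) or 35 weeks (8.0 months) later. Each relapse is dated at the next check, or at death if that comes first. Deaths without relapse are not modelled.

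**Results**, as ranges over the four medians and two treatment lengths (400,000 simulated remissions per scenario):

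| Only check after treatment | Mean delay of post-treatment relapses (months) | Rise in 12-month estimate (points) | Lengthening of median (months) |
|---|---|---|---|
| every 4 weeks | 0.43–0.44 | 0.1–0.8 | 0.0–0.7 |
| every 8 weeks | 0.82–0.84 | 0.1–0.8 | 0.1–1.1 |
| every 6 months | 2.06–2.24 | 2.9–9.1 | 0.1–2.8 |
| every 12 months | 3.03–3.41 | 7.6–14.4 | 0.1–4.2 |

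Part of the lengthening in the first two rows comes from the on-treatment schedule. The median hardly moves when it falls before treatment ends.

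**Hand check of the 12-month column.** A patient is wrongly counted as relapse-free at month 12 if relapse fell in the w months since the last check and the patient is still alive. With λ = ln 2 / median and μ = ln 2 / 3 = 0.2310:

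rise = λ/(μ − λ) × [exp(−12λ) − exp(−μw − λ(12 − w))]

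For a true median of 6, λ = 0.1155, the leading factor is 1 and exp(−12λ) = 0.250. With treatment ending at 4.6 months:

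- 12-monthly: last check at 4.6, w = 7.4; 0.250 − exp(−1.710 − 0.531) = 0.250 − 0.106 = 0.144, or 14.4 points.
- 6-monthly: last check at 10.6, w = 1.4; 0.250 − exp(−0.323 − 1.225) = 0.250 − 0.213 = 0.037, or 3.7 points.
- 8-weekly (1.84 months): last check at 4.6 + 4 × 1.84 = 11.96, w = 0.04; about 0.1 points.

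All three agree with the simulation for that scenario. The last one shows that the 12-month column depends on where month 12 falls between checks. If it fell just before an 8-week count (w = 1.84), the rise would be 0.250 − exp(−0.425 − 1.174) = 0.250 − 0.202 = 0.048, or 4.8 points. The mean delay does not depend on that alignment and is the safer comparison: 0.4 to 0.8 months against 2.1 to 3.4.

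**The case against.** A reader might infer that relapse is watched every 2 to 4 weeks on treatment and only every 6 to 12 months afterwards, so that CRd and PFS are lengthened by the schedule for everyone. The documents do not support that. The 2-to-4-week figure is the blood-count schedule, and the same sentence continues it at 4 to 8 weeks for patients on study. Like for like, the interval doubles. The 6-to-12-month contact also applies while on study, so it can run alongside the counts. Section 5.3(a) lets counts prompt a marrow or establish progression. Phone contact is allowed only for patients not attending.

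Nor does the plan say that relapse is dated at the contact. Section 8 refers to the date of disease relapse, and a call can retrieve the date of a diagnosis made elsewhere. The 6-to-12-month rows are therefore conditional, not a forecast.

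A reader might also set an inflated CRd beside the 14.7 months reported for the backbone in section 2.3. The plan proposes no such comparison, that series was in older patients with newly diagnosed AML, and its relapse surveillance is not described.

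Finally, no decision rests on these endpoints. They are secondary (section 1.0) in a single-arm study, and the phase II stopping rules use CR/CRi within two cycles and cycle 1 toxicity.

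All of this stands. It does not settle what relapse check applies to patients followed only by phone or under the umbrella protocol, or how their relapse and censoring dates are set.

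**Conclusion.** The point holds in a limited form, at low severity. Two post-treatment schedules are left unreconciled, and section 8 lets an unverified contact count as relapse-free follow-up.

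For patients who attend the 4-to-8-week counts, the mean delay is about 0.4 to 0.8 months. The 12-month estimate rises by under 1 point on the modelled calendar, and by somewhat more if month 12 falls late in an interval. If 6-to-12-month contact were the only check and relapse were dated at contact, the mean delay would be 2.1 to 3.4 months, the 12-month estimate would rise by about 3 to 14 points and the median by up to about 4 months. Those figures rest on the assumed exponential relapse times, the 3-month median from relapse to death, and treatment ending 4.6 to 8.0 months after CR. The effect on the whole cohort depends on how many patients are followed that way, which the documents do not say. If actual relapse dates are retrieved, most of the dating effect disappears.

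**What to change.** 1. In 5.3(b), reconcile the follow-up with 5.1(b) and 5.2(b): name the CBC already required every 4 to 8 weeks as the relapse check for responders on study, and accept local results. State what relapse information will be obtained for patients on the umbrella protocol.
2. In section 8, censor CRd and PFS at the last objective disease assessment (CBC or marrow) in place of last follow-up, so that a phone contact alone does not extend relapse-free time.
3. In section 8, date relapse at its first objective documentation, as 9.1.8 already does for relapse-free survival. When relapse is learned of by phone, retrieve the actual date.

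The cost is a few sentences of wording and some collection of local results. CRd and PFS may read slightly shorter. No new test, patients or interval-censored analysis is needed.
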